# **B-Research question:**

Does extraction of the upper third molars have a different impact than nonextraction on distalizing maxillary first molars in Class II adolescents?

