### **E]** Sample size calculation:

The sample size calculation is based on the findings of a pilot study, including three patients from each group, in which the upper first molar distalization amount was the primary outcome. The mean (standard deviation) values were 3.17(0.81) mm and 4.32 (0.79) mm in the TMP and TME groups, respectively. The effect size was 1. 437. With alpha level of 0.05 and a test power of 80%, the minimum estimated sample size was 18 patients (9 patients per group). Considering drop out a sample size of 11 per group is appropriate.

Sample size calculation is performed Using G\*Power version 3.1.9.2.

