### **C] Statistical Analysis:**

• The principal investigator will be responsible for the extraction of the required data from the CBCT taken before and after retraction as well as the study models taken at every follow up visit. The data will be sent to a specialized statistician.

• The specialized statistician will be responsible for the statistical analysis of the study by:

- 1. Presenting the data as mean, standard deviation (SD) and Standard error (SE) values.
- 2. Using Paired t-test to compare between the friction and the frictionless group of retraction as well as to compare between the pre-and post -treatment data for each group.

3. Using Anova test to determine the rate of anterior segment retraction.

4. Statistically evaluate the patient acceptance for both techniques.

• For this study, the specialized statistician will use IBM11 SPSS12 Statistics Version 20 for Windows to perform the required statistics.

• The significance level will be  $P \le 0.05$ . Highly significant variables are detected when P value is less than 0.01.

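### Within-arm pre/post tests sit beside the between-group test at the same threshold and are not labelled descriptive, although they do not address the effect of extraction

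*Combined protocol and SAP*

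**What the plan says.** Item 2 of the Statistical Analysis section (III, C) gives the paired t-test two jobs. The first is to compare the groups: "Using Paired t-test to compare between the friction and the frictionless group of retraction". The second is added in the same sentence: "as well as to compare between the pre-and post -treatment data for each group". The section sets one significance level, P ≤ 0.05, and a highly significant tier below 0.01. It does not separate the two uses of the test, rank one below the other, or mention confidence intervals.

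The Research question is a comparison of arms: "Does extraction of the upper third molars have a different impact than nonextraction on distalizing maxillary first molars in Class II adolescents". The null hypothesis is also between-arm, and the Study design section describes a 1:1 two-arm parallel trial. The Secondary objective is broader. It asks about the dental changes that accompany distalization in the buccal segment and the incisors.

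**The concern.** Under Clinical Procedure all patients get the same appliance and the same force, 300 g per side, and the distalization phase ends at a Class I molar relation or at eight months. A pre/post test inside one arm therefore shows whether teeth moved under that force. It carries no information about whether extraction changed the movement.

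The hazard lies in how two columns of within-arm P values are read. With 9 to 11 patients per arm, a modest change such as tipping, torque, rotation or incisor position can easily be significant in one arm and not in the other by chance. A reader, or the thesis itself, may then report that contrast as an effect of the third molars. Such a comparison has no 5% error control. What is at stake is the secondary conclusions about extraction, not the primary one.

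**Working it through.** **Inputs.** All come from the Sample size calculation section. Pilot distalization averaged 3.17 mm (SD 0.81) in the TMP group and 4.32 mm (SD 0.79) in the TME group, giving a standardised difference of 1.437. Alpha is 0.05 and power 80%. The plan needs 9 evaluable patients in each arm and recruits 11 to cover losses. The sidedness of the tests is not stated, so two-sided is assumed.

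**The plan's own figure.** d = (4.32 − 3.17) / √((0.81² + 0.79²)/2) = 1.15 / 0.800 = 1.437. A two-sided independent-samples t-test (noncentral t) has power 76.2% at 8 per arm and 81.6% at 9. The stated 9 per arm therefore reproduces, as an unpaired between-arm test. A one-sided test would need 7 per arm, and a paired design 6 pairs. Allowing for dropout, 9 / (1 − 2/11) = 11, so 11 per arm implies about 18% loss.

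**Chance of significance in one arm only when the arms are the same.** Let δ be the true mean change divided by the SD of the change, equal in both arms. The per-arm power p of the paired t-test comes from the noncentral t with n − 1 degrees of freedom and noncentrality δ√n. The arms are independent, so

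P(exactly one arm significant) = 2p(1 − p).

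Percentages below use unrounded p.

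| δ (SD) | p, n = 9 | one arm only, n = 9 | p, n = 11 | one arm only, n = 11 |
|---|---|---|---|---|
| 0 | 0.050 | 9.5% | 0.050 | 9.5% |
| 0.3 | 0.125 | 21.9% | 0.147 | 25.1% |
| 0.5 | 0.263 | 38.7% | 0.323 | 43.8% |
| 0.8 | 0.559 | 49.3% | 0.668 | 44.4% |
| 1.0 | 0.748 | 37.7% | 0.848 | 25.8% |
| 1.2 | 0.882 | 20.8% | 0.947 | 10.0% |
| 1.5 | 0.975 | 4.9% | 0.994 | 1.2% |

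A simulation of 40,000 trials per setting agrees (for example 44.0% at n = 11, δ = 0.5, and 9.4% at n = 9, δ = 0). In the same simulations an unpaired between-arm t-test rejected in 4.6% to 5.2% of trials in every setting.

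**Where the chance is 25% or more.** 2p(1 − p) ≥ 0.25 requires p between (1 − √0.5)/2 = 0.146 and (1 + √0.5)/2 = 0.854. That corresponds to δ from 0.34 to 1.15 at n = 9, and from 0.30 to 1.01 at n = 11. The maximum is 50%, at p = 0.5.

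**Primary outcome.** At the pilot values δ is 3.17/0.81 = 3.91 and 4.32/0.79 = 5.47. Power is about 1 in each arm, and the chance of significance in one arm only is about 0. The pilot SDs rest on three patients per group, but δ would have to fall to about 1.15 (n = 9) before the chance reached 25%.

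**Illustrations from the Literature Review.** These come from other appliances, so they show only the spread, at n = 9 / n = 11:

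- Bone-anchored pendulum, incisors, −0.1 (SD 1.7) mm: δ 0.06, 10% / 10%.
- Same study, incisors, −1.7 (SD 2.9) degrees: δ 0.59, 45% / 49%.
- Same study, first premolar, 2.7 (SD 1.6) mm: δ 1.69, 1.5% / 0.2%.
- Zygoma gear, first molar, 4.37 (SD 2.15) mm: δ 2.03, 0.1% / about 0.

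**The case against.** The strongest reply is that the plan does not do what is feared. A between-group comparison stands in the same sentence, and the pre/post tests are added to it. The research question, the null hypothesis and the sample size are all between-arm. Nothing says that arm-specific P values will be contrasted. This stands: a reader might infer that the trial means to judge extraction by which arm reaches significance, and the text does not support that. It only fails to exclude it. The planned between-group test also gives less protection than it should, because it is specified as paired and names groups that are not this trial's arms.

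The reply adds that within-arm change has a purpose of its own. The Secondary objective asks what dental changes accompany distalization, and the Rationale says the effects of mini-screws at this site have not been adequately evaluated. This also stands, and it is a reason to keep within-arm estimates with confidence intervals. It is not a reason to use their P values as evidence about extraction.

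Finally, item 2 does not say that every outcome is tested pre/post. Distalization rate, for one, has no pre-treatment value. That too is correct.

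**Conclusion.** The point holds in a conditional form. Within-arm tests are planned at the same threshold as the between-group test, are not labelled descriptive, and do not address extraction versus non-extraction. If their P values were contrasted, significance in one arm only would occur 25% to 50% of the time for outcomes with per-arm power of about 15% to 85% when the arms do not differ, against 5% for a valid between-arm test. Where nothing truly changes it is about 10%; at 1.5 SD and above it is under 5%.

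A reader might infer that a quarter to a half of this trial's outcomes will mislead in this way. The documents do not support that: they give no expected change or SD for the secondary outcomes, so the number in the affected range cannot be derived. Nor is the primary outcome at risk at the pilot values.

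The figures assume two-sided tests at 0.05, normally distributed changes, independent arms with the same true mean and SD of change, and one value per patient. The correction is worth making because it is specific and costs almost nothing.

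**What to change.** In item 2 of the Statistical Analysis section, replace the within-arm tests with wording such as:

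> In each arm, change from before to after distalization will be summarised as mean (SD) with a 95% CI, without a hypothesis test. Extraction and non-extraction will be compared only by the unpaired between-arm difference in change, with its 95% CI. Significance within an arm will not be used to compare arms.

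For distalization rate, which has no baseline, the between-arm difference is in the rate itself. Third-molar tipping and vertical change exist only where the third molars are kept, so for these the within-arm estimate with its CI is the whole result. Keeping within-arm estimates for all outcomes also serves the Secondary objective.

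The same item needs its between-group test changed from paired to unpaired and its group names corrected, so all of this can be one edit. It needs no further patients or measurements, and fewer tests are run. The price is the loss of the customary within-group P-value columns.

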# **Outcome measure(s):**

	Outcome name	Measuring device	Measuring unit
Primary outcome	The total anteroposterior distance moved by the maxillary first molars.	Digital models using 3- shape scanner and program.	mm

		CBCT images using Anatomage software.	mm
Secondary outcomes	1-Maxillary first molar distalization rate.	Digital models using 3 shape scanner and program.	mm/month
	2-Maxillary first molar rotation	Digital models using 3 shape scanner and program.	Degree
	3- Intermolar width	Digital models using 3 shape scanner and program.	mm
	4-Maxillary first molar tipping and torque	CBCT images using Anatomage software.	Degree
	5-Maxillary first molar vertical changes	CBCT images using Anatomage software	mm

	6- Total anteroposterior distance moved by maxillary first and second premolars.	Digital models using 3 shape scanner and program.	mm
	7- Maxillary second molar tipping.	CBCT images using Anatomage software	Degree
	8-Maxillary third molar tipping	CBCT images using Anatomage software	Degree
	9-Maxillary third molar vertical changes	CBCT images using Anatomage software	mm
	10-Maxillary four incisors anteroposterior and vertical linear measurements.	CBCT images using Anatomage software	mm
	11- Maxillary four incisors torque.	CBCT images using Anatomage software	mm

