#### 2) Secondary outcomes:

The secondary outcomes were the changes in upper first molars rotation, intermolar width, tipping, torque, and vertical position, the upper first molars distalization rate, the changes in the anteroposterior position of the upper first and second premolars, tipping of upper second molars, tipping and vertical position of the upper third molars, and anteroposterior, vertical, and torque changes of the upper incisors.

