### 3) Methods of measuring of all outcomes:

Linear and angular measurements will be made on the pre, post and follow-up digital models and on the pre-and post distalization CBCT to assess the dental changes in intervention group.

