### II) Assignment of interventions

### **A]** Sequence generation:

The supervisor of the study will apply Computer generated random numbers to randomly assign patients to group A (En-masse) or B (two steps) using Microsoft Office Excel 2007 sheet. The patient numbers will be written in the first column and the supervisor will select function RAND to generate the randomization number in the second column. These numbers will be sorted according to the randomization number so the first column numbers will be randomly distributed.

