### **C] Implementation**

At the time of intervention, the main operator will send the patient to the secretary's office. Then, the assigned employee will open the box and ask the patient to select one envelope. The main operator will contact the supervisor to know the order and then the main operator will allocate each patient to assign each participant for the corresponding intervention either (extraction or non-extraction) according to the list of codes of randomization.

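### The planned ANOVA is on the rate of anterior segment retraction, which is not an outcome of this trial, and the one rate outcome it does have, first-molar distalization rate, has no between-arm test

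*Combined protocol and SAP*

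**What the plan says.** The Statistical Analysis section has four items. Item 1 is descriptive (means, SDs, standard errors). Item 2 begins "Using Paired t-test to compare between the friction and the frictionless group of retraction" and adds a before-and-after comparison within each group. Item 3 is "Using Anova test to determine the rate of anterior segment retraction". Item 4 concerns patient acceptance.

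The outcome table lists, first among the secondary outcomes, "Maxillary first molar distalization rate", in mm/month from digital models. The secondary outcome text repeats it as "the upper first molars distalization rate". For the front teeth, the table lists "Maxillary four incisors anteroposterior and vertical linear measurements" and incisor torque, both from CBCT. The section on measurement methods places the CBCT readings "on the pre-and post distalization CBCT to assess the dental changes", that is, at two time points. The digital models are serial: impressions are taken at 4-weekly visits.

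The arms are named in the Implementation section, where each patient goes to the "corresponding intervention either (extraction or non-extraction" arm, and the Study design section describes two parallel groups.

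**The concern.** Item 3 is the only line in the plan that analyses a rate, and the rate it names belongs to a different kind of treatment. Taken literally, it asks for an analysis of a quantity that the trial does not define, while the rate that the trial does define has no test.

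The rate is not just the primary outcome in other units. The distalization phase may end when a Class I molar relation is reached or at eight months. If patients finish at different times, two patients with the same total movement can have different rates, so a test of total distance cannot stand in for a test of rate.

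Without a stated definition, unit and comparison, the statistician has to choose all three, possibly with the data in view. That makes any result on this outcome hard to treat as pre-specified.

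**Working it through.** **1. The plan's own figure.** The plan gives no figure for any rate. Its only calculation is for the amount of first-molar distalization, from pilot means (SD) of 3.17 (0.81) and 4.32 (0.79) mm.

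- Pooled SD = √((0.81² + 0.79²)/2) = 0.800 mm
- Effect size = (4.32 − 3.17)/0.800 = 1.15/0.800 = 1.437, as stated
- Two-sided independent t-test, alpha 0.05, power 80%: n = 8.67, rounded up to 9 per group, 18 in all, as stated
- Power is 81.6% with 9 per group and 89.3% with 11 per group

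So the sample size reproduces. It rests on an independent two-group comparison of distance and does not use item 3.

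**2. Is anterior segment retraction rate an outcome?** It is not in the outcome table, nor in the primary or secondary outcome text. The nearest entries are incisor position and torque. These are changes between two CBCT scans, with no serial CBCT readings between them.

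**3. Does any line test the molar rate between arms?**

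| Item | What it does | Does it test molar rate between arms? |
|---|---|---|
| 1 | Descriptive statistics | No; it describes only |
| 2, between groups | Paired t-test, friction against frictionless | No; these are not the trial's arms, and patients in parallel arms are not paired |
| 2, within group | Before against after treatment | No; a rate has no pre-treatment value |
| 3 | ANOVA on anterior retraction rate | No; different outcome, and no arm factor stated |
| 4 | Patient acceptance | No |

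**4. Is this an isolated slip?** No. The Sequence generation section has the supervisor "randomly assign patients to group A (En-masse) or B (two steps", which are not this trial's arms either. The data collection and harms sections also speak of retraction. The simplest explanation is text carried over and not adapted.

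**5. Would an ANOVA be wrong in itself?** Not necessarily. With one rate per patient and two arms, one-way ANOVA gives F = t², so it is the independent t-test. A repeated-measures ANOVA with arm as a between-patient factor also keeps the patient as the unit. An ANOVA that enters each visit as a separate independent row does not.

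To see how much the unit matters, trials with no arm effect were simulated, 10,000 per setting. None of the variance inputs is in the documents. The assumptions were 11 patients per arm, a baseline and eight equally spaced readings for everyone, linear movement, a mean rate of 0.468 mm/month (the average of 3.17/8 = 0.396 and 4.32/8 = 0.540), a between-patient rate SD of 0.10 mm/month, and a reading error SD of 0.1, 0.2 or 0.3 mm. False positives at P ≤ 0.05:

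| Analysis | Result across the three reading errors |
|---|---|
| One slope per patient, t-test | about 5% |
| Repeated measures, between-arm test | about 5% |
| Visits as independent rows, two-way, cumulative distance | 41% to 43% |
| Visits as independent rows, two-way, rate to date | 33% to 44% |
| Visits as independent rows, two-way, visit-to-visit increments | 24%, 5%, 0.8% |
| Visits as independent rows, one-way, cumulative distance | 7% to 11% |

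The analyses that keep the patient as the unit hold the nominal level. The row-wise layouts run from about 1% to about 45%, so the error can go in either direction.

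**The case against.** The strongest reply is that the intent can be recovered. The protocol uses retraction in several places as a leftover name for its own treatment phase, item 3 is a rate analysis, and the trial has only one rate. On that reading the defect is a wrong label. Much of this stands: item 3 probably was meant for the molar rate, and a suitable ANOVA would be valid. But changing the label alone does not complete the item. It would still name no arm factor, no time points and no unit, and determining a rate is not the same as comparing it between arms.

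A second reply is that item 2 is the larger problem, because it is the only between-group test for every outcome, the primary included. That is fair. The two items have the same cause and should be corrected together. Item 3 adds a gap of its own, because relabelling the groups in item 2 would still not define a rate.

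A reader might also infer that item 3 commits the trial to an analysis with a badly inflated false-positive rate. The documents do not support this. They plan no row-wise ANOVA, and the simulated error depends on layout and on assumed variances. The figures show why the unit should be stated; they do not measure the defect.

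Two further inferences also fail. One is that counting 4-week visits as months biases the rate: the timeline puts the final record at eight months, and any such scaling would affect both arms alike. The other is that visit dates are not kept: the data management section says what the data will include and need not be a complete list.

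**Conclusion.** The point holds on the text. Item 3 analyses something that is not an outcome, and the first-molar distalization rate has no inferential analysis that names it or compares the two arms. This is more than missing detail, because following the item as written does not produce a test of the rate outcome.

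Its size is modest. Item 3 affects one secondary outcome and leaves the sample size of 9 per group, raised to 11, unchanged. A reader might take this to mean that the primary analysis is sound; that does not follow, since item 2 has its own defect. No numerical bias can be attached to item 3, because the plan does not say which ANOVA would be run. The conclusion rests on the wording alone and does not depend on the simulation assumptions. The correction should be made, at the low end of that category.

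**What to change.** Replace item 3 with:

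*First-molar distalization rate (mm/month): one rate per patient, right and left first molars averaged, over that patient's actual time in distalization, compared between the extraction and non-extraction arms by an independent t-test.*

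State in advance which definition of rate applies: the slope over the serial models, or total mm divided by months. Either fits the outcome table. A mixed model or a repeated-measures ANOVA with the patient as the unit and arm as a between-patient factor is an acceptable alternative, if specified before the data are seen.

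In the same edit, correct item 2 so that it names this trial's arms and uses an unpaired comparison between them.

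The section on ending the distalization phase and item 8 of the participant timeline must also be reconciled. The first allows the phase to end at a Class I relation or at eight months; the second takes final records at eight months, at the appliance-removal visit. The rate needs one stated end point per patient. Which rule applies is for the investigators.

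The cost is a change of wording. It needs no new visits or measurements, uses models already planned, and can be run in the stated SPSS package.

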### **Assessors Reliability:**

• To achieve high reliability for measurements, the supervisor will choose a well experienced inter-examiner during the study.

• A training session will be provided for the examiners to ensure standard measurements techniques.

• Each examiner will complete the measurements on a model and will repeat the procedure after one week to assess the intra- and inter-examiner reliability.

• The supervisor will compare the measurements of the two assessors for disagreement with a difference of more than one millimetre.

• The supervisor will evaluate the amount of variation in measurements among and between examiners to test the performance of each assessor.

• The examiner with less reliability will receive additional training but will be replaced during the study.

• The specialized statistician will calibrate the intra and interexaminer reliability for the measurements of the study by the Intra-

31

class correlation coefficient (ICC). The closer the ICC to 1.0, the higher reliability between assessors. According to Fleiss:" ICC values between 0.7 and 0.9 represent good reliability." The kappa scores between study examiners will be calculated, a range of 0.60-0.80 will represent acceptable reliability.

### IV) Method Monitoring:

**A] Data Monitoring:** An independent Data Monitoring Committee (DMC) will monitor the results of the study. The Committee will include the trial's supervisors, who will periodically review the trial data and identify the need for any adjustments or modifications during the study.

**B] Interim Analysis**: no interim analysis will be performed during the study.

**CJHarm:** The main operator will document and report any harms or unwanted effects during the study intervention to the trial supervisors. Also, any unpleasant experience will be reported by the patient in the final questionnaire at the end of the retraction. The main operator will be responsible for the management of any adverse effects or unfavorable side effects resulting from the appliance.

**D]Auditing:** The supervisor will follow up and review the different interventions and resulting data. And he will periodically follow up the trial progress including recruitment of patients, allocation of participants to study groups; adherence to interventions and reporting of harms. A meeting with the senior

supervisor will be set every 3 months to monitor the progress of the study and the need for any adjustments.

